5.9.2. Progression-Free Survival

Progression-free survival (PFS) is defined as the time from the date of first dose until the date of radiographic documentation of progression (as defined by RECIST) based on investigator assessment or the date of death due to any cause, whichever is earlier. It is calculated as date of progression / censor – date of first treatment + 1.

[Table JGDR.5.1](#) lists rules for determining date of progression or censor for PFS.

Table JGDR.5.1. Rules for Determining Date of Progression or Censor for Progression-Free Survival

Rule	Situation	Date of Progression or Censor	Outcome
1	No baseline tumor assessment	Date of first dose	Censored
2	No postbaseline assessments and no death	Date of first dose	Censored
3	No documented progression and no death (with a postbaseline tumor assessment)	Date of last adequate tumor assessment	Censored
4	Patient lost to follow-up (or withdrew consent from study participation) before documented progression or death	Date of last adequate tumor assessment	Censored
5	Documented progression	Date of documented progression. If a tumor assessment was done on multiple days, use the earliest date for that visit.	Progressed
6	Death without documented progression	Date of death	Progressed
7	Documented progression or death after missing ≥ 2 consecutive postbaseline tumor assessments	Date of last adequate tumor assessment before missed assessments or date of first treatment, whichever is later.	Censored

Note: Progression-free survival and associated outcome is determined by the earliest of the dates above, if more than 1 situation applies. If there are multiple dates associated with 1 radiological tumor assessment, the assessment date will be set to the first date when the overall response is PD and the last date otherwise. A radiological tumor assessment is considered adequate if its response is among CR, PR, SD, or PD. Symptomatic deteriorations (that is, symptomatic progressions, which are not radiologically confirmed) will not be considered as disease progressions.

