5.9.3. Duration of Response

The duration of response (DoR) time is defined only for responders (patients with a confirmed CR or PR). It is measured from the date of first evidence of CR or PR to the date of objective progression or the date of death due to any cause, whichever is earlier. For clarity, the start date should be determined by the initial assessment of CR or PR, not the date of confirmation of CR or PR. It is calculated as date of progression or death – date of first response evaluation of CR or PR + 1.

Duration of response (DoR) will be censored according to the same rules as PFS, with the addition of the following rule: if a patient begins postdiscontinuation therapy, DoR will be censored on the day of the last response evaluation prior to the initiation of postdiscontinuation therapy.

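### SAP Rule 7 for PFS lets an old scan gap override a well-dated later event, and DoR inherits it; Rule 1 likewise drops known deaths (wrong as written, minor)

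*SAP*

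**What the plan says.** All the rules are in SAP 5.9.2 (Table JGDR.5.1 and its note) and SAP 5.9.3.

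- **Rule 7, situation:** "Documented progression or death after missing ≥ 2 consecutive postbaseline tumor assessments". The outcome is censored, and the date is: "Date of last adequate tumor assessment before missed assessments or date of first treatment, whichever is later".
- **Rule 5:** the patient counts as progressed. The date is: "Date of documented progression. If a tumor assessment was done on multiple days, use the earliest date for that visit".
- **Rule 6:** a death without documented progression is an event on the date of death.
- **Rule 3:** a patient with post-baseline scans and no event is censored at the last adequate scan.
- **Rules 1 and 2:** both censor at first dose. Rule 2 (no post-baseline scan) applies only if the patient has not died. Rule 1 (no baseline scan) has no such condition.
- **Note:** "Progression-free survival and associated outcome is determined by the earliest of the dates above, if more than 1 situation applies".
- **DoR (5.9.3):** it starts at the first CR or PR of a confirmed response, and "will be censored according to the same rules as PFS". One rule is added, for the start of post-discontinuation therapy.

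The text of 5.9.2 makes death from any cause a PFS event. Neither document narrows Rule 7 elsewhere.

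**The concern.** Rule 7 exists for the case where the progression date is uncertain because the scans just before the event are missing. Once an adequate scan after the gap shows no progression, that uncertainty is gone and the later event is dated as well as any other. Rule 7 does not stop at that point. Any earlier double gap satisfies its wording, however many adequate scans follow.

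Three things are at stake:

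- A real event, and the documented progression-free time before it, can be replaced by an early censoring date that the data contradict.
- The same gap is ignored in a patient who has no event, because Rule 3 then applies. Whether the gap counts therefore depends on the later outcome, which makes the censoring informative.
- DoR can end before it begins. That would force an unplanned repair after the data have been seen.

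Rule 1 has a related fault. A treated patient with no baseline scan who dies has a known PFS event by definition, yet is censored at first dose.

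**Working it through.** The plan states no event count, precision or missed-scan rate for PFS or DoR, so there is no figure of its own to reproduce. The check applies the rules to example patients and then asks how often the problem would arise.

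**Inputs.** Scans are every 6 weeks from the start of treatment (protocol Table JGDR.2), so the Week w scan falls on Day 7w + 1. For PFS: "It is calculated as date of progression / censor – date of first treatment + 1". For DoR: end date − date of first response + 1. A month is 365/12 days (SAP 5.2.2).

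**Example A: a gap, then adequate scans, then progression.** SD at Week 6, Weeks 12 and 18 missed, PR at Weeks 24, 30 and 36, PD at Week 42.

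- Rule 5 date: 7 × 42 + 1 = Day 295, progressed.
- Rule 7 date: 7 × 6 + 1 = Day 43, censored.
- The note takes the earlier date. PFS is censored at 43 ÷ (365/12) = 1.4 months, instead of an event at 295 ÷ (365/12) = 9.7 months.
- First response is on Day 7 × 24 + 1 = 169, so DoR = 43 − 169 + 1 = −125 days.
- With the same gap, PR also at Week 42 and death at Week 44 (Day 309), Rule 7 still gives Day 43 and overrides Rule 6.
- With the same gap, PR at Week 42 and no event, Rule 3 censors at Day 295. Only patients with an event are moved back.

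**Example B: a gap at the start.** Weeks 6 and 12 missed, PR from Week 18 (Day 127) through Week 36, PD at Week 42.

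- Rule 7 censors at the date of first treatment, Day 1.
- DoR = 1 − 127 + 1 = −125 days. That it equals the value in Example A is a coincidence of the two schedules.

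**With Rule 7 limited to the gap immediately before the event.** Both patients progress on Day 295. DoR is 295 − 169 + 1 = 127 days in A and 295 − 127 + 1 = 169 days in B. A true pre-event gap keeps its present result: with PR at Weeks 6 and 12, Weeks 18 and 24 missed and PD at Week 30, the patient is censored on Day 85 and DoR is 85 − 43 + 1 = 43 days.

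**Rule 1.** For a patient with no baseline scan who dies, Rule 6 gives an event on the date of death and Rule 1 gives censoring at first dose. The note selects first dose.

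**How often.** These are assumptions, not figures from the documents: exponential PFS with a 6-month median, scans every 42 days, and each scan missed independently with probability 5% or 10%, or in clusters (8%, rising to 40% after a miss). Only progressions were simulated, not deaths. The approximate share of progressions censored solely because of a non-adjacent gap is:

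| Length of scanning | 5% missed | 10% missed | 8%/40% clustered |
|---|---|---|---|
| 9 months | 0.2% | 0.6–0.7% | 1.5% |
| 12 months | 0.3% | 1.1% | 2.9% |
| 18 months | 0.6% | 2.1% | 5.4% |

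Even if all 30 patients on the recommended regimen progressed, the clustered case would affect 30 × 0.015 = 0.5, 30 × 0.029 = 0.9 or 30 × 0.054 = 1.6 patients. In separate 18-month runs with a median PFS of 6 or 9 months and 5%, 10% or 20% independent misses, the Kaplan-Meier median was the same under both readings.

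**The case against.** **This is an ambiguity, and a programmer may read it the usual way.** Dating the censoring at the last adequate scan before the missed ones fits a gap that ends in the event, and many analysts would supply that meaning unprompted. This stands in part: a reader might infer that the analysis will certainly be run the harmful way, and the documents do not show that. But a result that is right only through an unwritten condition is not prespecified.

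**The note is not the root fault.** A reader might blame the earliest-date note and want an explicit order of rules in its place. The documents do not support that. Even with the gap immediately before the event, Rule 7 applies together with Rule 5 or Rule 6, and it is the note that lets Rule 7 prevail. An order that placed progression above Rule 1 would also count a recorded PD with no baseline scan as an event, although change from baseline cannot then be judged. This objection stands in full.

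**DoR could be read on its own clock.** Carrying the PFS rules over might be taken to mean applying them from first response. That is sensible, but SAP 5.9.3 does not say it.

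**Follow-up may be too short.** Study completion is 30 days after Dose Confirmation patients finish combination therapy (protocol 5.3). With six 21-day cycles and no delays, that is 6 × 21 + 30 = 156 days for the last patient. A non-adjacent gap before a progression needs four scheduled scans, the fourth at Week 24. After treatment, scans become 3-monthly once two 6-weekly scans are done (protocol Table JGDR.3). This rightly lowers the expected count for late-enrolled patients. It does not make the fault impossible for them: after missed scans at Weeks 6 and 12 and an adequate scan at Week 18 (Day 127), a death before Day 156 would be censored at Day 1. Earlier patients are followed longer.

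**Rule 1 cases should be rare.** Baseline imaging and evaluable disease are required, so this stands as to frequency. Efficacy is nevertheless analysed in all treated patients regardless of eligibility (SAP 5.2.1 and 5.9).

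**Conclusion.** The rules are wrong as written, and the matter is minor. Rule 7 lacks an adjacency condition, DoR inherits the gap and can be negative, and Rule 1 contradicts the PFS definition for deaths. These findings follow from the text and need no assumption.

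The size does rest on assumptions: about 0.2–1.5% of progressions with 9 months of scans, 0.3–2.9% with 12 and 0.6–5.4% with 18, which usually means 0 to 1 of 30 patients. A reader might infer that one or two of 30 will be lost. That needs 18 months of 6-weekly scans for everyone plus clustered misses. The protocol does not give every patient that follow-up, and the clustering rate has no source in the documents.

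A reader might also infer that the PFS results would mislead. The simulated median did not move, SAP 5.9 rules out efficacy hypothesis testing, and the dose thresholds in protocol Table JGDR.7 use DLT counts. The practical risk is an occasional discarded event, or an impossible DoR that must be repaired ad hoc.

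**What to change.** 1. **Rule 7:** reword the situation to documented progression or death where the two or more scheduled assessments immediately before it were missed, with no adequate assessment in between. Censor at the last adequate assessment before that gap, or at first treatment if later. It would help to say whether a non-evaluable scan counts as missed.
2. **DoR (5.9.3):** state that only assessments missed after the first response count, and that DoR is never censored before the first response.
3. **Rule 1:** add the condition that the patient has not died, as in Rule 2. Keep a patient with no baseline scan and a recorded PD but no death censored at first dose. Also state that if such a patient later dies, the death is the event and not the uninterpretable PD.
4. **Note:** keep it. Once Rules 1 and 7 are narrowed it does what is needed, and no replacement order of rules is required.

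The cost is a few lines in the SAP and the matching programming. It needs no new data, visits or patients.

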5.9.3. Duration of Response

The duration of response (DoR) time is defined only for responders (patients with a confirmed CR or PR). It is measured from the date of first evidence of CR or PR to the date of objective progression or the date of death due to any cause, whichever is earlier. For clarity, the start date should be determined by the initial assessment of CR or PR, not the date of confirmation of CR or PR. It is calculated as date of progression or death – date of first response evaluation of CR or PR + 1.

Duration of response (DoR) will be censored according to the same rules as PFS, with the addition of the following rule: if a patient begins postdiscontinuation therapy, DoR will be censored on the day of the last response evaluation prior to the initiation of postdiscontinuation therapy.

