Radiologic imaging and measurement of palpable or visible lesions	X	X*	
*For patients whose disease has not progressed: Perform q 6 weeks × 2, then q 3 mo until:
 
 the patient has objective disease progression according to RECIST 1.1 or the study's primary/final analysis 
Perform using the same method used at baseline and throughout the study.
 
For patients who have had objective disease progression: Radiologic tests and measurement of palpable or visible lesions are no longer required; these patients should be followed up for OS and collection of post-study treatment anticancer therapy information collection as indicated below.

Collection of survival information		X	Perform q 2 mo (±7 days) for the first 2 years after discontinuation from study treatment and q 6 mo (±14 days) thereafter until death or study completion. If an in-person visit is not possible, confirm survival by contacting the patient directly via phone.
Collection of post-study treatment anticancer therapy information	X	X	Perform q 2 mo (±7 days) for the first 2 years after discontinuation from study treatment and q 6 mo (±14 days) thereafter until death or study completion.
ECG	X	X	
 All patients should have a 12-lead ECG performed at short-term follow-up. Patients should also have a 12-lead ECG performed approximately 6 months (±7 days) and 12 months (±7 days) after the end of treatment with doxorubicin and ifosfamide.

Procedure	Short-Term Follow-Up ^a	Long-Term Follow-Up	Instructions
Visit	801	802-8XX	
Echocardiogram and/or MUGA scan		X	Perform at 6 months (± 7 days) and 12 months (± 7 days) after the end of treatment with doxorubicin and ifosfamide. Echocardiograms/MUGA scans may be discontinued if the patient begins another anticancer therapy. Perform additional evaluations in the setting of cardiac symptoms and/or at the discretion of the investigator.
Hematology	X		See Appendix 3 . To be performed locally for patient management and centrally for analysis purposes.
Coagulation	X		See Appendix 3 . To be performed locally.
Clinical chemistry	X		See Appendix 3 . To be performed locally for patient management and centrally for analysis purposes.
Urinalysis	X		See Appendix 3 . To be performed locally.
Sample collection			For all sample collection, see Appendix 4 .
Pharmacodynamics			
Pharmacokinetics			
Immunogenicity			
Pharmacogenetics			
Other biomarkers			

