8.1. Discontinuation from Study Treatment

Patients will be discontinued from study treatment under the following circumstances:

- the patient is enrolled in any other clinical trial involving an investigational product or any other type of medical research judged not to be scientifically or medically compatible with this study
- the patient becomes pregnant during the study
- the patient is significantly noncompliant with study procedures and/or treatment
- the patient demonstrates disease progression
- the patient has unacceptable toxicity
- the patient, for any reason, requires treatment with another therapeutic agent that has been demonstrated to be effective for treatment of the study indication. Discontinuation from study treatment will occur prior to introduction of the new agent
- the patient undergoes surgical tumor resection
- the investigator decides that the patient should be discontinued from study treatment
- the patient requests to be discontinued from study treatment
- the patient's designee (for example, legal guardian or caregiver) requests that the patient be discontinued from study treatment

Patients who are discontinued from study treatment will have follow-up procedures performed as shown in the Schedule of Activities (Section 2).

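### SAP 5.9.3 does not say whether a responder who progresses and then starts new therapy is a duration-of-response event or is censored

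*SAP*

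**What the plan says.** SAP 5.9.3 measures DoR in confirmed responders from the first CR or PR "to the date of objective progression or the date of death due to any cause, whichever is earlier". It then sets the censoring: "Duration of response (DoR) will be censored according to the same rules as PFS, with the addition of the following rule". The added rule reads "if a patient begins postdiscontinuation therapy, DoR will be censored on the day of the last response evaluation prior to" the start of that therapy. Its only trigger is that the therapy begins.

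The inherited rules are in Table JGDR.5.1 of SAP 5.9.2. Rule 5 makes documented progression an event on its date. Rule 4 (loss to follow-up or withdrawn consent) applies only "before documented progression or death". The note under the table sets precedence: "Progression-free survival and associated outcome is determined by the earliest of the dates above, if more than 1 situation applies". The same note counts a PD result as an adequate assessment.

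Two parts of the protocol fix the usual order of events. Section 8.1 lists "the patient demonstrates disease progression" among the reasons for stopping study treatment. Table JGDR.3 in Section 2 says of patients with objective progression: "Radiologic tests and measurement of palpable or visible lesions are no longer required". It continues: "these patients should be followed up for OS and collection of post-study treatment anticancer therapy information collection as indicated below".

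**The concern.** The added rule is presumably meant for a responder who moves to another therapy while still in response, so that the new therapy's effect is not credited to study treatment. As worded, it also covers a responder who has already progressed and then starts next-line therapy. That patient has completed a DoR interval, yet the sentence says the interval is censored.

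Two programmers could follow the SAP faithfully and code this patient in opposite ways. If the literal coding is used, events are removed from the patients who supply most of them, and the Kaplan-Meier median rises or is not reached. DoR is a named secondary efficacy endpoint in Protocol Table JGDR.5, and the Kaplan-Meier median is its planned summary (Protocol 10.3.1, SAP 5.9).

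**Working it through.** **Step 1. Apply the rules.** Let P be the date of the progression scan and T the date new therapy starts.

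| Situation | Rule 5 | Added DoR rule | Earliest-date note, if inherited |
|---|---|---|---|
| Therapy starts before any progression | Not yet met at T | Censored at last evaluation before T | Censored, as intended |
| P before T, with a further evaluation between them | Event at P | Censored after P | P is earlier: event |
| P before T, progression scan is the last evaluation | Event at P | Censored at P | Dates equal: not resolved |

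The third row is probably the usual one, because Table JGDR.3 requires no imaging after progression while new anticancer therapy is still recorded. In that row the recorded time is P under either reading. Only the event flag differs.

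**Step 2. Size under the literal reading.** The SAP gives no DoR figure to reproduce. The share q of progressions followed by new therapy is not in the documents, so it is varied as an assumption.

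Let DoR be exponential with hazard λ, so the median is m = ln 2/λ. If a random share q of progressions is recoded as censored, the remaining event hazard is (1-q)λ. The Kaplan-Meier median then estimates ln 2/[(1-q)λ] = m/(1-q).

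- q = 50%: 1/0.5 = 2.0 times
- q = 70%: 1/0.3 = 3.3 times
- q = 90%: 1/0.1 = 10 times

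**Step 3. Check with the scan schedule.** The simulation used 20,000 responders, scans every 6 weeks (Protocol Table JGDR.5; 42/(365/12) = 1.38 months) and administrative censoring uniform over 12 to 24 months (assumption). Progression is dated at the next scan, so a true median of 6 months appears as 5 × 1.38 = 6.9.

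| Assumed true median | PD as event | q = 30% | q = 50% | q = 70% | q = 90% |
|---|---|---|---|---|---|
| 4 months | 4.1 | 6.9 | 9.7 | 15.2 | not reached |
| 6 months | 6.9 | 9.7 | 13.8 | 22.1 | not reached |
| 9 months | 9.7 | 13.8 | 19.3 | not reached | not reached |

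In the 6-month row, the share of responders with an event falls from about 85% to 59%, 42%, 25% and 8%. The ratios 13.8/6.9 = 2.0 and 22.1/6.9 = 3.2 agree with Step 2.

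**Step 4. Small numbers.** This simulation took 8 responders, a true median of 6 months, follow-up uniform over 3 to 18 months (all assumptions) and 8,000 replicates per setting. Mean events fall from 5.3 to 2.6, 1.6 and 0.5 at q = 50%, 70% and 90%. The chance that the median is not reached rises from 6% to about 48%, 71% and 91%; repeat runs agree within about one percentage point.

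**Step 5. Progression takes precedence.** Every patient in the third row of Step 1 is then an event at P. The results are those in the PD-as-event column, and the bias is zero.

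**The case against.** The strongest answer is that SAP 5.9.3 should be read as a whole. Its definition ends DoR at objective progression or death. Rule 5 is inherited, and the added rule supplements the PFS rules without repealing them. A responder with documented progression has met the endpoint before any later therapy begins. A rule that removed most of an endpoint's own events would make little sense. This stands as the likelier intent.

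A reader might therefore infer too much from the added sentence taken alone: that the SAP orders every progressor who starts new therapy to be censored, and that the reported DoR will be inflated. The documents do not support that. The definition and Rule 5 point to an event, and where an evaluation falls between progression and new therapy, the earliest-date note, if inherited, also gives an event.

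The size is also conditional. None of q, the number of responders, the true median or the follow-up is given as a design value. A high q is not established: collection of post-study therapy ends at study completion (Table JGDR.3), and long-term follow-up stops when continued access begins (Protocol 7.9.1). SAP 5.9 analyses efficacy within each cohort of about 15. At the background response rate of about 25% in Protocol 3.1.1, that is 15 × 0.25 = 3.75, or about 4 responders. With 4 responders even the correct coding yields only about 2.7 events under the Step 4 assumptions, so the median would be fragile anyway.

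None of this breaks the tie. Likely intent is not a stated precedence, and the sentence says without exception that DoR is censored. Rule 4 shows that the authors wrote the limiting condition where they wanted it.

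**Conclusion.** The point holds as an unresolved conflict between event and censoring. It affects responders whose progression scan is the last evaluation before new therapy.

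The effect ranges from none, if progression takes precedence, to a median multiplied by 1/(1-q), if the added sentence is programmed literally. That is 2.0 times at q = 50% and 3.3 times at q = 70%, with a growing chance that the median is not reached. These figures rest on an exponential DoR, on q being unrelated to the timing of progression, and on assumed values of q.

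The reach is limited. SAP 5.9 states that the study is not designed for efficacy hypothesis tests. PFS has no new-therapy rule, and ORR and OS do not use this one. Cohort progression and the recommended regimen rest on DLT and other safety data (Protocol 7.2.2.1 and 9.4.2). The wording should be corrected before DoR is programmed, but it does not threaten the trial's primary conclusions.

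**What to change.** Replace the added rule in SAP 5.9.3 with: *if a patient begins postdiscontinuation therapy before documented objective progression or death, DoR will be censored on the day of the last adequate tumor assessment before that therapy; progression documented on or before the start of that therapy is an event.*

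The first clause restricts the rule to its evident purpose. The second states the precedence that the earliest-date note cannot supply. Using adequate tumor assessment ties the date to the term that Table JGDR.5.1 defines.

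The cost is one sentence in a SAP revision and a check of the DoR derivation code. It needs no new data and no patient burden. It should not need a protocol amendment, since Protocol 10.3 requires one only when a principal feature changes.
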